QTc	corrected QT interval
SAE	serious adverse event
SOP	Standard Operating Procedure
SS	Safety Set
T3	triiodothyronine
T4	thyroxine
TEAE	treatment-emergent adverse event
TSH	thyroid stimulating hormone
ULN	upper limit of normal
VNS	vagus nerve stimulation

1 SUMMARY

SP0966 is a Phase 2, multicenter, open-label exploratory study designed to assess the safety and preliminary efficacy of oral lacosamide (LCM, Vimpat[®]; SPM 927; previously referred to as harkoseride; [R]-2-acetamido-N-benzyl-3-ethoxypropionamide, ADD 234037) as adjunctive therapy for epilepsy syndromes associated with generalized seizures in pediatric subjects ≥ 1 month to < 18 years of age. The objectives of this study are to evaluate the safety and tolerability of LCM when added to 1 to 3 concomitant antiepileptic drugs (AEDs) in pediatric subjects with epilepsy syndromes associated with generalized (Type II) seizures, and to obtain preliminary efficacy data of LCM on seizure frequency in pediatric epilepsy syndromes associated with generalized seizures.

The primary variables in this study are changes in the count of generalized spike-wave discharges and change in days with any generalized seizures (absence, myoclonic, clonic, tonic, tonic-clonic, atonic, and partial evolving to secondarily generalized) from the Baseline Period to the Maintenance Period. The above variables reference partial seizures evolving to secondarily generalized seizures. While these partial seizures will be summarized as a part of the analysis, subjects must have a diagnosis of uncontrolled epilepsy with generalized seizures (Type II) according to the International Classification of Epileptic Seizures (1981) (see Section 17.1) to possibly be eligible for study participation. In addition to the Type II seizures, subjects with a current diagnosis of mixed seizure disorder(s), including both Type I and Type II seizures, are also eligible. Subjects with exclusively absence (Type IIA1) or atypical absence (Type IIA2) seizures are not eligible. Other variables to be assessed include measures of efficacy, plasma concentrations, and other measures of safety.

Approximately 50 subjects will be enrolled in this study across approximately 50 sites in Europe and North America, and other regions as deemed necessary.

The study will begin with subject screening at Visit 1 and will consist of a 6-week prospective Baseline Period where seizure frequency will be captured through daily seizure diaries. At the end of the Baseline Period, subjects will commence a 6-week Titration Period at Visit 2, where subjects will initiate treatment with LCM (LCM dosing flexibility allowed based on tolerability). Subjects weighing < 50 kg will begin treatment on LCM oral solution 2mg/kg/day, and subjects weighing ≥ 50 kg will begin treatment on LCM tablets 100mg/day (subjects weighing ≥ 50 kg who are unable or unwilling to swallow tablets can be dispensed LCM oral solution instead). The dose will be titrated to a level to optimize tolerability and seizure control, not to exceed 12mg/kg/day (oral solution) for subjects weighing < 50 kg or 600mg/day (tablets/oral solution) for subjects weighing ≥ 50 kg. At the end of the Titration Period (Visit 6), a 12-week Maintenance Period will begin. Subjects must titrate to at least 4mg/kg/day for subjects weighing < 50 kg or 200mg/day (tablets/oral solution) for subjects weighing ≥ 50 kg in order to enter the Maintenance Period. The LCM dose will remain stable throughout the Maintenance Period. Subjects who require a change in dose during the Maintenance Period will be withdrawn from the study. Subjects who require a change in formulation during the Maintenance Period should consult the medical monitor to assess if the subject can continue in the study.

The end of the Maintenance Period will be Visit 9, or, if subjects withdraw early, the Early Termination Visit. Subjects may be eligible for participation in an additional open-label study (SP848) if they have completed the Maintenance Period and are taking a minimum dose of 4mg/kg/day for subjects weighing <50kg or 200mg/day (tablets/oral solution) for subjects weighing ≥50kg. Subjects who do not complete the full 12 weeks of the Maintenance Period may still be eligible to enter the SP848 open-label study after consultation with the medical monitor. Subjects who choose not to participate in the additional open-label study or subjects who discontinue LCM due to other reasons will enter a 2- to 4-week Taper Period followed by a Safety Follow-Up Visit 2 weeks (±2 days) after the final dose of LCM and a Safety Follow-Up Telephone Contact 30 days (-1/+3 days) after the final dose of LCM. Taper of LCM may not be required for some subjects who discontinue study medication prematurely, depending on the treatment option selected by the investigator in consultation with the subject and/or parent/legal representative.

2 INTRODUCTION

Epilepsy is the second most prevalent neurological disorder in the world. More than 40 million people suffer from epilepsy—about 1% of the world's population (Dicke, 1999). Although some forms of epilepsy may respond to surgical treatment and others may not require any treatment at all, most patients with epilepsy require appropriate pharmacological therapy (Perucca, 1996). The Institute of Medicine of the National Academies recently provided a review of the burdens of epilepsy, global incidence and prevalence of epilepsy, classification systems for seizure types and syndromes, gaps in information about epilepsy, and general recommendations (Institute of Medicine, 2012). Several new options for the medical treatment of epilepsy have been introduced, including novel AEDs and vagus nerve stimulation (VNS).

The classification of epilepsies in pediatric subjects was described in 1989 by the Commission on Classification and Terminology of the International League Against Epilepsy (Aicardi, 1994). Seizures are categorized based on whether the onset is focal or generalized and whether the disorder is idiopathic, symptomatic, or cryptogenic. Specific syndromes are further classified according to a number of criteria including seizure type, cause, anatomy, precipitating factors, age of onset, and sometimes prognosis.

The newer AEDs differ from older agents in several important ways, including mechanism of action, spectrum of activity, and pharmacokinetic (PK) characteristics (Herman and Pedley, 1998). However, >30% of patients have inadequate seizure control on currently available AEDs or experience significant adverse drug effects (Beghi and Sander, 2008). Therefore, a need remains for AEDs with improved effectiveness and tolerability (Shorvon, 2009).

Among the newer AEDs, only 6 (gabapentin, lamotrigine, oxcarbazepine, topiramate, levetiracetam, and perampanel) have successfully demonstrated efficacy as adjunctive therapy in pediatric subjects with difficult to treat partial-onset seizures (Appleton et al, 1999; Duchowny et al, 1999; Elterman et al, 1999; Glauser et al, 2000; Glauser et al, 2006; Rheims and Ryvlin, 2013). Despite the availability of new AEDs, more than 25% of pediatric patients have inadequate seizure control on currently available AEDs or experience significant adverse drug effects (Hadjiloizou and Bourgeois, 2007).

Lacosamide belongs to a novel class of functionalized amino acids. It has minimal protein binding and effect on cytochrome P450 enzyme system function (reducing the risk of drug-drug interactions), high oral bioavailability, and a half-life of approximately 13 hours (in adults), which allows a twice daily (bid) dose regimen. It also displays dose-proportional PK following administration over a range of doses up to 800mg in adults. Lacosamide's mode of action is proposed to be mediated by a selective enhancement of slow inactivation of voltage-gated sodium channels which may explain the immediate anticonvulsant effects of LCM (Errington et al, 2008).

Lacosamide has been approved as adjunctive therapy in the treatment of partial-onset seizures with or without secondary generalization in patients 16 years of age and older in the EU (oral tablets, oral solution, and solution for intravenous [iv] infusion) and as adjunctive therapy in the treatment of partial-onset seizures in patients 17 years of age and older in the USA (oral tablets, oral solution, and solution for iv infusion). The oral solution and the film-coated tablet formulations are suitable for oral administration to pediatric patients.

Bioequivalence has been shown between the tablet and oral solution formulations, comparing 2 tablets of LCM 100mg and the oral solution containing LCM 200mg, after single-dose administration in healthy subjects. The PK of LCM and its major metabolite, SPM 12809 (O-desmethyl-LCM), in plasma, urine, and saliva were identical or very similar after single oral doses of LCM 200mg administered as tablets or as oral solution.

In the clinical development program for LCM, safety and tolerability of multiple doses of up to LCM 400mg bid (800mg/day) were evaluated in 868 unique subjects who received oral and/or iv LCM in Phase 1 studies. The safety and efficacy of LCM has also been evaluated in Phase 2/3 studies as adjunctive oral therapy in 1427 adult subjects with partial-onset seizures, as oral monotherapy in 425 adult subjects with partial-onset seizures, as adjunctive oral therapy in 49 subjects with primary generalized tonic-clonic seizures, and as oral monotherapy in 2435 adult subjects in other indications (eg, neuropathic pain, osteoarthritis, fibromyalgia, and migraine prophylaxis). In addition, LCM solution for infusion was evaluated as short-term replacement therapy in a subset of subjects with partial-onset seizures (199 patients) who were receiving adjunctive LCM tablets.

Three double-blind, placebo-controlled, multicenter studies (SP667, SP754, and SP755) in 1308 adult subjects, aged 16 to 70 years, established the efficacy of oral LCM as adjunctive therapy (1 to 3 concomitant AEDs) in subjects with difficult to control partial-onset seizures. In these studies, LCM was initiated at a dose of 100mg/day (in 2 divided doses) and escalated to the randomized dose (200mg/day, 400mg/day, or 600mg/day) in 100mg/day per week increments.

When oral LCM was administered as adjunctive therapy at doses up to 600mg/day in the 3 double-blind, placebo-controlled, multicenter studies in subjects with partial-onset seizures, the most frequently reported treatment-emergent adverse events (TEAEs) were central nervous system- and gastrointestinal-associated events. A dose relationship was seen for the most frequently reported common TEAEs, including dizziness, headache, nausea, and diplopia. The nature and frequency of adverse events (AEs) were comparable to adjunctive therapy with other marketed AEDs. Safety evaluations support the further development of LCM as an AED.

UCB has completed a Phase 2, open-label safety study (SP0961) of adjunctive LCM treatment for primary generalized tonic-clonic seizures in 49 subjects ≥ 16 years of age with idiopathic generalized epilepsy. The results of SP0961 showed reductions in primary generalized tonic-clonic seizure frequency and myoclonic seizure days, with a small reduction in absence seizure days. A minority of subjects ($\sim 10\%$) showed an increase in absence seizures (reported as TEAEs) that, in this uncontrolled study, cannot be distinguished between the drug versus the natural course of the disease. The AE profile was similar to that of adjunctive LCM for the treatment of subjects with partial-onset seizures, with the exception of seizure-related AEs.

Further information on LCM preclinical results, as well as the PK, efficacy, and safety profiles, can be obtained from the current version of the LCM Investigator's Brochure.

SP0966 is a Phase 2, multicenter, open-label exploratory study designed to assess the safety and preliminary efficacy of oral LCM as adjunctive therapy for epilepsy syndromes associated with generalized (Type II) seizures in pediatric subjects ≥ 1 month to < 18 years of age.

3 STUDY OBJECTIVE(S)

- To evaluate the safety and tolerability of LCM when added to 1 to 3 concomitant AEDs in pediatric subjects with epilepsy syndromes associated with generalized seizures
- To obtain preliminary efficacy data of LCM on seizure frequency in pediatric epilepsy syndromes associated with generalized seizures
- An additional objective is to evaluate the PK of LCM in subjects ≥ 1 month to < 18 years of age.

4 STUDY VARIABLES

The variables below reference partial seizures evolving to secondarily generalized seizures. While these partial seizures will be summarized as a part of the analysis, subjects must meet eligibility criteria to be applicable for the study (see inclusion criterion 4 and exclusion criteria 5 and 6 for applicable subjects).

4.1 Safety variables

4.1.1 Primary safety variables

The primary variables assessing safety are:

- Changes in count of generalized spike-wave discharges on 24-hour ambulatory electroencephalogram (EEG) from Visit 2 to Visit 6
- Change in days with any generalized seizures (absence, myoclonic, clonic, tonic, tonic-clonic, atonic, partial evolving to secondarily generalized) per 28 days from the Baseline Period to the Maintenance Period

The assessment of seizure days will be based on the seizure diary.

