6 SELECTION AND WITHDRAWAL OF SUBJECTS

6.1 Inclusion criteria

To be eligible to participate in this study, all of the following criteria must be met:

1. A signed informed consent has been obtained from the parent/legal representative and assent has been obtained from the subject (when possible or as required according to local Institutional Review Boards [IRBs]/Independent Ethics Committees [IECs]).
2. Subject and/or caregiver (which may be a parent, a legal representative, or other caregiver) are willing and able to comply with all study requirements including maintaining a daily seizure diary.
3. Subject is male or female, ≥1 month to <18 years of age. For preterm infants <1 year old, the corrected gestational age should be used when determining eligibility. The generally accepted definition of corrected gestational age, which is calculated by subtracting the number of weeks born before 37 weeks of gestation from the chronological age, will be used for this study.

4. Subject has a diagnosis of uncontrolled epilepsy with generalized seizures (Type II) according to the International Classification of Epileptic Seizures (1981) (see Section 17.1). The underlying epilepsy syndrome should be documented. Diagnosis should have been established by clinical history and an EEG with generalized spike-wave discharges. Documentation of the EEG finding of generalized spike waves (EEG recording or a report) is required. The EEG should have been performed no more than 18 months prior to Visit 1 (with no change to diagnosis or seizure types during this time).
5. Subject must have experienced 2 or more events (typical generalized seizures associated with diagnosed epilepsy syndrome) within the 6-week prospective Baseline Period.
6. Subject is on a stable dosage regimen of 1 to 3 AEDs. The daily dosage regimen of concomitant AED therapy must be kept constant for a period of at least 4 weeks prior to the Baseline Period.
7. Vagal nerve stimulation is allowed and will not be counted as a concomitant AED. The VNS device must be implanted for at least 6 months before Visit 1 and the device settings must be stable for at least 4 weeks before Visit 1 and be kept stable during the Baseline Period and the Treatment Period. Use of the VNS device magnet is allowed.
8. Body weight at Visit 1 is at least 4kg for infants.
9. Females of childbearing potential must have a negative pregnancy test at Visit 1.

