17 APPENDICES

17.1 International Classification of Epileptic Seizures (1981)

Adapted from the International Classification of Epileptic Seizures (1981)

I. Partial seizures (focal, local)

A. Simple partial seizures (consciousness not impaired)

1. With motor signs
2. With somatosensory or special sensory symptoms (simple hallucinations, eg, tingling, light flashes, buzzing)
3. With autonomic symptoms or signs (including epigastric sensation, pallor, sweating, flushing, piloerection, and pupillary dilatation)
4. With psychic symptoms (disturbance of higher cerebral function). These symptoms rarely occur without impairment of consciousness and are much more commonly experienced as complex partial seizures.

B. Complex partial seizures (with impairment of consciousness: may sometimes begin with simple symptomatology)

C. Partial seizures evolving to secondarily generalized seizures (this may be generalized tonic-clonic, tonic, or clonic)

II. Generalized seizures (convulsive or non-convulsive)

A. Absence seizures

B. Myoclonic seizures - Myoclonic jerks (single or multiple)

C. Clonic seizures

D. Tonic seizures

E. Tonic-clonic seizures

F. Atonic seizures - (Astatic)

Unclassified epileptic seizures

Includes all seizures that cannot be classified because of inadequate or incomplete data and some that defy classification in hitherto described categories. This includes some neonatal seizures, eg, rhythmic eye movements, chewing, and swimming movements.

Status epilepticus (prolonged partial or generalized seizures without recovery between attacks)

Commission on Classification and Terminology of the International League Against Epilepsy. Proposal for revised clinical and electroencephalographic classification of epileptic seizures. *Epilepsia*. 1981;22:489-501.

17.2 Protocol Amendment 1

Rationale for the amendment

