### 8.1.2 Generalized seizures

Days with any generalized seizures per 28 days (GSD/28d) will be based on the seizure diary and will be derived separately for the Baseline Period, the Titration Period, and the Maintenance Period. Basis for the calculation will be the number of days with at least 1 generalized seizure (GSD) (absence, myoclonic, clonic, tonic, tonic clonic, atonic, partial evolving to secondarily generalized) during the considered study period and the number of days in the considered study period for which seizure information was provided (D):

$$\text{GSD/28d} = \text{GSD} \times (28/\text{D})$$

The days with any generalized seizures per 28 days will only be derived for subjects who completed or discontinued during the respective study period. For subjects who discontinued during the Titration Period, the missing value of the Maintenance Period will be imputed as described in Section 4.2.

Descriptive statistics will be provided for actual values and changes from Baseline for days with any generalized seizures per 28 days by study period. This summary will be repeated by syndrome subgroups (as described in Section 4.8).

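### The by-syndrome seizure-day and worsening tables use only a composite that includes Type IC seizures, so a fall in IC-only days can hide a rise in Type II days

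*Protocol*

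**What the plan says.** - **Variable.** Protocol 4.1.1 defines the second primary safety variable as "Change in days with any generalized seizures (absence, myoclonic, clonic, tonic, tonic-clonic, atonic, partial evolving to secondarily generalized) per 28 days"; the comparison is of Maintenance with Baseline. SAP 8.1.2 builds it from the "number of days with at least 1 generalized seizure (GSD) (absence, myoclonic, clonic, tonic, tonic clonic, atonic, partial evolving to secondarily generalized" list, scaled to 28 days. A day counts once, whichever listed type occurred.
- **Classification.** Inclusion criterion 4 (Protocol 6.1) requires a "diagnosis of uncontrolled epilepsy with generalized seizures (Type II" in the 1981 classification. Protocol 17.1 places "C. Partial seizures evolving to secondarily generalized seizures" under class I, partial seizures, not class II.
- **Who can contribute IC days.** Protocol 5.1 admits children with mixed Type I and Type II disorders. Exclusion criterion 5 removes only those with purely partial-onset seizures (or exclusively absence seizures).
- **Disclosure.** Protocol 1 and 4 state that these partial seizures are part of the analysis even though eligibility requires Type II. Neither gives a reason.
- **Tables.** SAP 9.1.1 (Full Analysis Set) lists the composite and each of the six Type II types, without a syndrome breakdown. It has no Type II total and no IC row, although IC days are a declared variable in Protocol 4.2 and SAP 2.2.2.1. SAP 8.1.2 repeats the composite by syndrome. SAP 9.2 gives, by syndrome, the proportion with at least a 50% reduction, the proportions with more than a 30% and a 50% increase, and the percent change, all for generalized seizures with the derivation referred to 8.1.2.

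**The concern.** Protocol 5.4 says the study should help to set aside syndromes in which LCM shows no clear benefit or may provoke exacerbations. Protocol 2 reports that about 10% of subjects in an uncontrolled study of idiopathic generalized epilepsy had more absence seizures. The open safety question is therefore about Type II seizures, syndrome by syndrome.

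The by-syndrome tables answer it with a count that also contains IC days. Protocol 2 describes LCM as approved in the EU, from age 16, as "adjunctive therapy in the treatment of partial-onset seizures with or without secondary generalization", so IC days might plausibly fall on treatment. If they do, a child whose Type II seizures worsen can appear stable, and the syndrome's worsening proportion is too low.

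**Working it through.** The plan gives no figure to reproduce: the study is descriptive and has no formal sample-size calculation. The check is whether the SAP's own derivation allows the masking, and how much is needed.

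**Inputs.** From the documents: GSD/28d = GSD × (28/D), with a day counted once (SAP 8.1.2); worsening thresholds of more than 30% and 50% (SAP 9.2); syndrome subgroups shown from 4 subjects (SAP 4.8). Assumed, because the documents give nothing: the numbers of Type II and IC-only days and their changes.

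**One child, non-overlapping days per 28.**
- Type II: 10 to 14, which is 14/10 − 1 = +40%. This exceeds 30%.
- IC-only: 6 to 3, which is −50%.
- Composite: (10 + 6) = 16 to (14 + 3) = 17, which is 17/16 − 1 = +6.25%. This is not counted as worse.

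**Same daily frequencies, with the two kinds of day overlapping independently.**
- Baseline: 28 × [1 − (18/28)(22/28)] = 13.9.
- Maintenance: 28 × [1 − (14/28)(25/28)] = 15.5.
- Change: +11.9%. Overlap weakens the masking, but the child is still below 30%.

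**General form.** Let f be the share of baseline composite days that are IC-only, r the relative fall in those days, and w the relative rise in Type II days. Then

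composite change = (1 − f)w − f·r,

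so a Type II rise is fully hidden when w ≤ f·r/(1 − f).

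| f | hidden w, r = 25% | hidden w, r = 50% |
|---|---|---|
| 0.2 | 6.2% | 12.5% |
| 0.3 | 10.7% | 21.4% |
| 0.5 | 25% | 50% |

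A true Type II rise of 50% reads as 30% or less once f reaches (0.5 − 0.3)/(0.5 + r). That is 0.20 for r = 50% and 0.27 for r = 25%.

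**Small subgroups.** In a displayed syndrome of 4 children, one child like the example changes the worsening proportion by 1/4 = 25 percentage points. The mean change differs between the two versions by (4 − 1)/4 = 0.75 day.

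**Can the reader undo it from the tables?** No. One day may carry several seizure types, so the separate counts in SAP 9.1.1 do not sum to a Type II total. That section also omits IC days and does not call for a syndrome breakdown.

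**The case against.** A reader might infer that the protocol contradicts itself by using two definitions of generalized seizure. The documents do not support that. An endpoint need not match the eligibility definition, the components are spelled out wherever the variable is defined, and Protocol 1 and 4 disclose the choice. There may also be a reason for it: Protocol 17.1 notes that IC seizures can take tonic-clonic, tonic or clonic form, and the count comes from a diary kept by subjects or caregivers.

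A reader might also infer that Type II worsening would go unseen. It would not. SAP 9.1.1 shows each Type II type free of IC by definition. The EEG variables have tables of increases of at least 30% and 50% at Visit 6 (SAP 8.1.1 and 8.2.1). Clinically significant increases in seizure frequency are recordable as adverse events (Protocol 11.1.1), which are tabulated by syndrome (SAP 8.2.2). Listings of all data are planned (SAP 3.1).

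Finally, it is tempting to say that LCM is known to work on these seizures, or to calculate a shift in the group mean. Protocol 2 gives approvals from age 16 or 17 and efficacy in subjects aged 16 to 70, with no paediatric or IC-specific effect. Mixed disorder also covers Type IA and IB seizures, which the composite does not count, so the share with mixed disorder is not the share with IC seizures.

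All of this stands and limits the point. What remains is the gap in seizure-day tables by syndrome: 9.1.1 is not broken down by syndrome, and the EEG outputs count discharges rather than seizures, with the primary comparison ending before Maintenance.

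**Conclusion.** The point holds at the syndrome level only. Under the SAP's derivation, a child with IC seizures and a clear Type II rise can fall below the worsening threshold, and no planned seizure-day table by syndrome would show it. In the illustration, +40% becomes +6%.

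This rests on assumed day counts and on IC-only days falling during treatment. The documents give neither an effect on IC seizures in children nor the share of subjects who have them. The group-level size is therefore unknown, and small if few such children enrol. The study is single-arm and descriptive with no formal decision rule, so severity is minor: a supportive analysis is missing, and the primary variable is not defective.

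**What to change.** 1. Keep the composite as the declared primary variable.
2. In SAP 8.1.2 and 9.2, repeat the same summaries (value, change, percent change, 50%-reduction proportion, 30% and 50% increase proportions), overall and by syndrome, for days with any Type II seizure (IIA to IIF). Show them beside the composite and read both when judging exacerbation.
3. Add days with Type IC seizures to the SAP 9.1.1 list, so that the declared variable is reported.

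**Cost.** One derived variable and a few extra tables. The diary already records seizure type (Protocol 9.1), so no new data are needed. Caregivers may record some IC seizures as tonic-clonic, so the Type II version is not clean either. That is the reason to show the two side by side rather than replace one with the other.
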